6.3. Lifestyle Restrictions

6.3.1. Meals and Dietary Restrictions

No meal or dietary restrictions are required for participation in this study. Danirixin must be taken with food. Specific dosing instructions will be provided in the Study Reference Manual (SRM) and will be provided to all study participants.

6.3.2. Activity

Participants should abstain from strenuous exercise for 24 hours before each blood collection for clinical laboratory tests.

6.4. Screen Failures

Screen failures are defined as participants who consent to participate in the clinical study but are not subsequently randomized in the study. A minimal set of screen failure information is required to ensure transparent reporting of screen failure participants to meet the Consolidated Standards of Reporting Trials (CONSORT) publishing requirements and to respond to queries from regulatory authorities. Minimal information includes demography, screen failure details, eligibility criteria and any serious adverse events (SAEs).

Individuals who do not meet the criteria for participation in this study (screen failure) may be rescreened up to two additional times if the investigator judges the participant can meet the eligibility criteria. Any rescreened participant must satisfy all of the protocol specified inclusion/exclusion requirements at the re-screening visit. Rescreened participants should be assigned a new participant number at the time of rescreening.

6.5. Run In Failures

A run in failure is defined as a participant who consents to participate in the clinical study, satisfies all eligibility criteria, but who does not properly complete the required baseline assessments for the daily EXACT diary, daily rescue medication use, and the physical activity monitoring portion of PROactive baseline (if selected to participate in the physical activity subgroup) over 7 days beginning with Visit 2. A participant who is selected to participate in the physical activity subgroup and does not complete the baseline physical activity monitoring portion of PROactive baseline but does complete the daily EXACT diary and daily rescue medication use baseline assessments will still be eligible for participation in the study but will not be included in the physical activity

subgroup. Participants who are run in failures will not be randomized to any study treatment and are not eligible for rescreening.

A successful EXACT baseline assessment is defined as completion of all 14 questions of the EXACT questionnaire on at least 4 of the 7 days. Successful rescue medication use recording is defined as recording of rescue medication use in the daily diary on at least 4 of the 7 days along with electronic data capture from the MDI sensor device. For participants in the physical activity subgroup a successful baseline determination is defined as recording of physical activity for at least 8 hours per day on at least 3 of the 7 days and completion of the PROactive questionnaire at Visit 3.

During the time period between Visit 2 and Visit 3 if a participant has a moderate or severe COPD exacerbation (one that requires treatment with systemic corticosteroids and/or antibiotics or requires hospitalization), the patient should not be randomized and should be withdrawn. In this case, the participant may be rescreened at a later date if the investigator judges the participant can meet the eligibility criteria. A participant with a mild COPD exacerbation would not need to be withdrawn.

7. TREATMENTS

Study treatment is defined as any investigational treatment(s), marketed product(s), placebo or medical device(s) intended to be administered to a study participant according to the study protocol.

7.1. Treatments Administered

Table 3 Treatments Administered

Study Treatment Name:	Danirixin (GSK1325756H, the hydrobromide hemihydrate salt)	Placebo
Dosage formulation:	White Film coated tablets (oval or round shaped). Refer to Investigator's Brochure for presentation and excipients	White Film coated tablets (oval or round shaped). Refer to Investigator's Brochure for presentation and excipients
Unit dose strength(s)/Dosage level(s):	5, 10, 25, 35 and 50 mg (of free base equivalent)	N/A
Route of Administration	Oral	Oral
Dosing instructions:	One tablet to be taken twice daily with food	One tablet to be taken twice daily with food

Study Treatment Name:	Danirixin (GSK1325756H, the hydrobromide hemihydrate salt)	Placebo
Packaging and Labeling	Study Treatment will be provided in a HDPE bottle with desiccant. Each bottle will be labeled as required per country requirement.	Study Treatment will be provided in a HDPE bottle with desiccant. Each bottle will be labeled as required per country requirement.
Manufacturer	GSK	GSK

7.1.1. Medical Devices

- Subject to availability and any local restrictions on use, MDI sensor devices (manufactured by and purchased from Propeller Health) are being provided by GSK for this study. These devices are fitted onto rescue medication MDI devices to electronically record rescue medication usage. The MDI sensor devices have US FDA 510(k) clearance to market (Class II medical device) and European Union CE marking (Class I medical device).
- Subject to availability and any local restrictions on use, ActiGraph GT9X physical activity monitors (manufactured by and purchased from ActiGraph, LLC) are being provided by GSK for the subset of participants that will be included in the physical activity monitoring subgroup. The device is a tri-axial accelerometer. The participant wears the devices for the period of time that physical activity is being monitored.
- Additional descriptive information and instructions for the eMDI and physical activity monitoring devices are provided in the SRM.
- GSK medical device incidents, including those resulting from malfunctions of the device, must be detected, documented, and reported by the Investigator throughout the study (see Section 9.2).

7.2. Dose Modification

No individual participant dose modifications or adjustments are allowed.

7.3. Method of Treatment Assignment

- This study will use an Interactive Web Response System (IWRS). All participants will be centrally randomized using the IWRS. Before the study is initiated, the log in information and directions for the IWRS will be provided to each site.

- Participant randomization will be stratified by smoking status (i.e. current smoker or former smoker).
- Study treatment will be dispensed to participants at the study visits summarized in the SOA.
- Returned study treatment should not be re-dispensed to any participant.

7.4. Blinding

This will be a double-blind (sponsor open) study. Study participants, all study site staff, and all members of the GSK study team, with the exception of the study statistics and programming team, will be blinded to individual participant treatment assignment. As defined in the study charter and RAP, defined and named members of the GSK study team will have access to unblinded, aggregate summaries of study treatment results.

A participant will be withdrawn if the participant's treatment code is unblinded by the investigator or treating physician. The primary reason for discontinuation (the event or condition which led to the unblinding) will be recorded in the CRF.

GSK's Global Clinical Safety and Pharmacovigilance (GCSP) staff may unblind the treatment assignment for any participant with an SAE. If the SAE requires that an expedited regulatory report be sent to one or more regulatory agencies, a copy of the report, identifying the participant's treatment assignment, may be sent to investigators in accordance with local regulations and/or GSK policy.

7.5. Preparation/Handling/Storage/Accountability

- The investigator or designee must confirm and document appropriate temperature conditions have been maintained during transit for all study treatment received and any discrepancies are reported and resolved before use of the study treatment.
- Only participants enrolled in the study may receive study treatment and only authorized site staff may supply or administer study treatment. All study treatments must be stored in a secure, environmentally controlled, and monitored (manual or automated) area in accordance with the labeled storage conditions with access limited to the investigator and authorized site staff.
- The investigator, institution, or the head of the medical institution (where applicable) is responsible for study treatment accountability, reconciliation, and record maintenance (ie, receipt, reconciliation, and final disposition of records).
- Further guidance and information for the final disposition of unused study treatment are provided in the SRM.
- Precaution will be taken to avoid direct contact with the study treatment. Under normal conditions of handling and administration, study treatment is not expected to pose significant safety risks to site staff. In the case of unintentional occupational exposure notify the monitor, Medical Monitor and/or GSK study contact.

- A Material Safety Data Sheet (MSDS)/equivalent document describing occupational hazards and recommended handling precautions either will be provided to the investigator, where this is required by local laws, or is available upon request from GSK.

7.6. Treatment Compliance

- When participants are dosed at the site, they will receive study treatment directly from the investigator or designee, under medical supervision. The date and time of each dose administered in the clinic will be recorded in the source documents. The dose of study treatment and study participant identification will be confirmed at the time of dosing by a member of the study site staff other than the person administering the study treatment.
- When participants self-administer study treatment(s) at home, compliance with study treatment administration will be assessed through querying the participant during the site visits and documented in the source documents and CRF. In addition, participants will be asked to confirm study administration each day in the daily diary.
- Study participants who are not compliant with study treatment administration requirements should be re-educated on the importance of treatment compliance. Every effort should be made to keep participants in the study. Participants who continue to be non-compliant after several attempts to re-educate may be discontinued after consultation with the GSK study team.
- A record of the number of tablets dispensed to and taken by each participant must be maintained and reconciled with study treatment and compliance records. Treatment start and stop dates, including dates for treatment delays and/or dose reductions will also be recorded in the CRF.

7.7. Concomitant Therapy

Any medication or vaccine (including over-the-counter or prescription medicines, vitamins, and/or herbal supplements) that the participant is receiving at the time of enrolment or receives during the study must be recorded along with:

- reason for use
- dates of administration including start and end dates
- dosage information including dose and frequency

The Medical Monitor should be contacted if there are any questions regarding concomitant or prior therapy.

The following COPD medications are permitted during the study, at the discretion of the GSK Medical Monitor and/or Investigator:

- Inhaled COPD maintenance medications (e.g. long acting bronchodilator medications (i.e. LAMA, LABA) and long-acting bronchodilator combination

therapies (e.g. LAMA/LABA) and long-acting bronchodilator/inhaled steroid combination (ICS) therapies (e.g. LABA/ICS, LAMA/LABA/ICS)

- Short courses of oral corticosteroids and/or antibiotics (including macrolides) are permitted for the acute treatment of exacerbations of COPD and should not exceed 21 days. This use must be recorded as an HCRU exacerbation event.

The following medications are prohibited from the screening visit until after completion of the follow up visit:

- Chronic use of macrolide antibiotics for the prevention of COPD exacerbations. Examples of chronic use include daily or two-three times per week for at least 3 months.
- Oral or injectable CYP3A4 or BCRP substrates with narrow therapeutic index (CYP3A4 substrates include, but are not limited to, alfentanil, cyclosporine, dihydroergotamine, ergotamine, fentanyl, pimozide, quinidine, sirolimus, tacrolimus, and theophylline; BCRP substrates include, but are not limited to, topotecan.
- Phosphodiesterase-4 inhibitors (e.g. roflumilast)
- Broad spectrum phosphodiesterase inhibitors (e.g. theophylline)
- Chronic use of systemic corticosteroids, i.e. long term (i.e. greater than 3 weeks), daily use of systemic corticosteroids. Chronic use of intranasal, intraocular and topical (for dermatological conditions) corticosteroids is allowed.

GSK will not supply rescue medication. Participants may continue to use and should obtain rescue medication(s) through via their usual route. The following rescue medications may be used:

- Short acting beta agonists (SABA) (e.g., albuterol/salbutamol)
- Short acting muscarinic antagonists (SAMA) (e.g., ipratropium)
- Short acting combination (SABA/SAMA) bronchodilations, (e.g. Duoneb, Combivent)

The use of rescue medications is allowable at any time during the study. Participants should record in the daily e-diary the number of puffs of rescue medication(s) over each 24 hour period. Data from the MDI sensor device will be electronically captured and transmitted to GSK.

Oxygen for intermittent use or PRN therapy ≤ 15 hours per day is allowed. Long term oxygen therapy or nocturnal oxygen therapy required for >15 hours is excluded throughout the study.

Annual influenza vaccine is recommended for patients with COPD but is not required for participation in this study. Influenza vaccination is permitted during the study and should be based on applicable local or national guidelines. Pneumococcal vaccine may also be administered, when indicated, based on applicable local or national guidelines.

Additional vaccinations may be administered when indicated. Any vaccination administered during the study should be recorded as a concomitant therapy.

7.8. Treatment after the End of the Study

The investigator is responsible for ensuring that consideration has been given to the post-study care of the participant.

GSK will not provide post-study treatment. There are no plans to provide the study treatment for compassionate use following study completion.

[figure not shown]
8. DISCONTINUATION CRITERIA

8.1. Discontinuation of Study Treatment

8.1.1. Liver Chemistry Stopping Criteria

Liver chemistry stopping and increased monitoring criteria have been designed to assure participant safety and evaluate liver event etiology (in alignment with the FDA premarketing clinical liver safety guidance). These protocol guidelines are in alignment with FDA premarketing clinical liver safety guidance [FDA, 2009].

Discontinuation of study treatment for abnormal liver tests should be considered by the investigator when a participant meets one of the conditions outlined in the algorithm below or if the investigator believes that it is in the best interest of the participant.

Liver Safety Required Actions and Follow up Assessments Section can be found in [Appendix 7](#).

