Impairment of host defense.	
Host defense has not been studied directly in nonclinical studies. However, data in nonclinical species have not identified an increased risk of infection with danirixin. Nonclinical studies in mice and ferrets with two CXCR2 antagonists in the same chemical class as danirixin have not shown an increase in infections in challenge models (e.g., influenza viral load). Secondary bacterial infections after viral infection have not been directly evaluated in nonclinical studies.
 
The data from clinical studies including healthy participants, COPD and influenza patients thus far show no evidence that participants taking danirixin have an increased infection rate compared with participants taking placebo.
 
Neutropenia has been reported in clinical trials of other CXCR2 antagonists. No instances of neutropenia have been reported in nonclinical studies with danirixin. In healthy volunteer studies and a phase 2a study in patients with Influenza (GSK Study
	
Monitoring of neutrophil count.
 
Stopping criteria: in participants with a confirmed absolute neutrophil count $\leq 0.5 \times 10^9/L$ product will be discontinued and neutrophil count will be monitored until return to normal. Participants may be restarted on study treatment as detailed in Appendix 9.
 
Ongoing assessment of AE/SAEs related to infection.
 
Closely monitor, collect information on and characterize infection events such as pneumonia, and use adjudication as appropriate.

Investigational Product (IP) [Danirixin, GSK1325756]		
Potential Risk of Clinical Significance	Summary of Data/Rationale for Risk	Mitigation Strategy
	
201682, GlaxoSmithKline Document No. 2014N205875_00), decreased neutrophil counts have been observed in subjects receiving either placebo or danirixin; no instances of danirixin-related neutropenia have been reported in clinical studies to date. In healthy subjects, the data are confounded by the observation of low neutrophil counts before dosing or at follow-up, and were not dose-related, while in patients with influenza, neutrophil counts recovered while receiving danirixin, coincident with resolution of the viral infection. There have been no reports of neutrophil count decreases below the lower limit of normal in patients with COPD who were treated with danirixin for one year. These data support the conclusion that a causal association of neutropenia with danirixin cannot be definitively established.
	

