8.1.3. Neutrophil Stopping Criteria

A participant with a peripheral blood neutrophil count $\leq 0.5 \times 10^9/L$ that is confirmed on repeat testing will be instructed to suspend dosing. The neutrophil count should be monitored daily until it returns to within the baseline value, as detailed in [Appendix 9](#).

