8.1.5. Study Treatment Restart

Study treatment restart after liver chemistry stopping criteria are met by any participant in this study is not allowed. Refer to [Appendix 7](#) for full guidance for required actions and follow-up assessments to undertake if liver stopping criteria are met.

Study treatment restart after neutrophil stopping criteria are met can be considered once the neutrophil count has returned to within baseline and provided that no more than 14 days have elapsed since study medication was halted. The Investigator must obtain approval from the GSK Medical Monitor prior to restarting study treatment. See [Appendix 9](#) for the procedure to be followed for study treatment restart after neutrophil stopping criteria are met.

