12.7. Appendix 7: Liver Safety: Required Actions and Follow-up Assessments

Phase II liver chemistry stopping and increased monitoring criteria have been designed to assure participant safety and evaluate liver event etiology

Phase II liver chemistry stopping criteria and required follow up assessments

Liver Chemistry Stopping Criteria	
ALT-absolute	ALT \geq 5xULN
ALT Increase	ALT \geq 3xULN persists for \geq 4 weeks
Bilirubin^{1, 2}	ALT \geq 3xULN and bilirubin \geq 2xULN (>35% direct bilirubin)
INR²	ALT \geq 3xULN and INR>1.5, if INR measured
Cannot Monitor	ALT \geq 3xULN and cannot be monitored weekly for 4 weeks
Symptomatic³	ALT \geq 3xULN associated with symptoms (new or worsening) believed to be related to liver injury or hypersensitivity
Required Actions and Follow up Assessments	
Actions	Follow Up Assessments

 • Immediately discontinue study treatment • Report the event to GSK within 24 hours • Complete the liver event CRF and complete an SAE data collection tool if the event also meets the criteria for an SAE² • Perform liver chemistry event follow up assessments • Monitor the participant until liver chemistries resolve, stabilize, or return to within baseline (see MONITORING below) • Do not restart/rechallenge participant with study treatment unless allowed per protocol and GSK Medical Governance approval is granted (see below) • If restart/rechallenge not allowed per protocol or not granted, permanently 	
 • Viral hepatitis serology⁴ • Obtain INR and recheck with each liver chemistry assessment until the transaminases values show downward trend • Obtain blood sample for pharmacokinetic (PK) analysis, up to 72 h after last dose⁵ • Serum creatine phosphokinase (CPK) and lactate dehydrogenase (LDH). • Fractionate bilirubin, if total bilirubin \geq 2xULN • Obtain complete blood count with differential to assess eosinophilia • Record the appearance or worsening of clinical symptoms of

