12.9. Appendix 9: Neutrophil Safety and Study Treatment Restart

Neutrophil Stopping Criteria: Absolute neutrophil count (ANC) $\leq 0.5 \times 10^9 /L$	
Required Actions and Follow up Assessments	
Actions	Follow Up Assessments

 • Immediately discontinue study treatment • Report the event to GSK within 24 hours • Complete an SAE data collection tool if the event also meets the criteria for an SAE • Monitor the participant until neutrophil count stabilizes or returns to within baseline (see MONITORING below) • Do not restart participant with study treatment unless allowed per protocol and GSK Medical Governance approval is granted (see RESTART below) 
MONITORING:
 
 • Treatment of any suspected infections¹ • Repeat CBC within 24 hrs • Monitor CBC daily until neutrophil count resolves, stabilizes or returns to within baseline 	
 • Record the appearance or worsening of any clinical symptoms on the AE report form¹ • Obtain blood sample for pharmacokinetic (PK) analysis within 12 hours after last dose² • Record use of concomitant medications on the concomitant medications report form
RESTART	

 • Restart of study medication must be approved by the GSK Medical Monitor • Restart may be attempted ONLY if all three criteria are met: 
 • The neutrophil count is $\geq 1.5 \times 10^9/L$ for at least 48 hours • At least 7 days have elapsed since the suspension of study treatment • No sign or symptom of associated infection has been identified 	
 • Check the CBC within 24-48 hours after re-starting study medication, monitor twice weekly for two weeks, and monthly thereafter. • If the ANC drops below $1.0 \times 10^9/L$ on restart, the participant should be permanently discontinued from study treatment and withdrawn from the study.

1. New or worsening symptoms believed to be related to neutropenia such as (but not limited to): sudden onset of fever or malaise, stomatitis, odynophagia, periodontal infection, skin abscesses, signs or symptoms of sinusitis and otitis, symptoms of pneumonia (eg, cough, dyspnea), perirectal pain and irritation, hypotension or signs of septic shock.

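### The liver and neutrophil stopping rules in Protocol Section 8.1 do not match Appendices 7 and 9, and the neutrophil restart conditions and approver are split between two places

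*Protocol*

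**What the plan says.** **Liver, stopping.** Protocol Section 8.1.1 states: "Discontinuation of study treatment for abnormal liver tests should be considered by the investigator when a participant meets one of the conditions" of its algorithm, or if the investigator thinks it in the participant's interest. It then points to Appendix 7. The stopping table in Appendix 7 has, as its first required action, "Immediately discontinue study treatment".

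**Liver, restart.** Section 8.1.5: "Study treatment restart after liver chemistry stopping criteria are met by any participant in this study is not allowed". Appendix 7: "Do not restart/rechallenge participant with study treatment unless allowed per protocol and GSK Medical Governance approval is granted".

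**Neutrophils, stopping.** Under Section 8.1.3, a participant with a count of 0.5 x 10^9/L or below "that is confirmed on repeat testing will be instructed to suspend dosing". The risk table in Section 3.3.1 also refers to a confirmed count, after which "product will be discontinued and neutrophil count will be monitored until return to normal". Appendix 9 gives the same threshold without a confirmation step, uses the same immediate-discontinuation instruction as Appendix 7, and lists a repeat blood count within 24 hours under monitoring.

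**Neutrophils, restart.** Section 8.1.5 opens the possibility of restart "once the neutrophil count has returned to within baseline and provided that no more than 14 days have elapsed since study medication was halted", with Medical Monitor approval, and refers to Appendix 9 for the procedure. Appendix 9 has three criteria: a count of at least 1.5 x 10^9/L for 48 hours, "At least 7 days have elapsed since the suspension of study treatment", and no associated infection. Its actions list names GSK Medical Governance as approver; its restart box names the Medical Monitor.

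**The concern.** A stopping rule should give one action for one laboratory result. Here a site reading Section 8.1 and a site reading the appendices can act differently on the same liver result, or on the same first neutrophil count. Section 9 of the protocol allows no waivers and treats adherence as required, so a site that follows one passage faithfully can be in breach of the other.

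The study has no independent data monitoring committee (Section 5.1), and the neutrophil rule is part of the stated mitigation for host-defence risk in Section 3.3.1. The liver rule is described in Section 8.1.1 as there to protect participants. Uneven application by site is therefore mainly a participant-safety and conduct matter.

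**Working it through.** No sample size, power or event count is involved, so the check is a side-by-side reading of the current protocol text. The superseded protocol version reprinted behind it was not used.

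1. **Liver stop, example ALT at or above 5 x ULN.**
   - Section 8.1.1: the investigator considers stopping.
   - Appendix 7: treatment stops immediately, as a required action.
   - Appendix 7 has a separate table for participants who may stay on treatment under closer monitoring (ALT from 3 to below 5 x ULN, bilirubin below 2 x ULN, no symptoms, weekly monitoring possible). Its stopping table therefore leaves no discretion.
   - Result: discretionary against mandatory. Conflict.

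2. **Liver restart.** Section 8.1.5 prohibits it. Appendix 7 prohibits it unless the protocol allows it, and otherwise requires permanent discontinuation. Result: the same outcome. No conflict.

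3. **Neutrophil stop, first count at or below 0.5 x 10^9/L, repeat not yet available.**
   - Sections 8.1.3 and 3.3.1: the condition for action is a confirmed count, so it is not yet met.
   - Appendix 9: discontinue now; repeat within 24 hours.
   - Result: different action during the wait for the repeat. Conflict, confined to that interval.
   - The end point for monitoring also differs: within baseline (8.1.3), normal (3.3.1), or resolved, stable or within baseline (Appendix 9).

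4. **Neutrophil restart, timing in days since dosing stopped.**
   - Section 8.1.5 alone: days 0 to 14.
   - Appendix 9 alone: day 7 onward, no upper limit stated.
   - Both together: days 7 to 14.
   - Result: the permitted window depends on whether the two lists are cumulative, which neither passage says.

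5. **Neutrophil restart, count and infection.** Section 8.1.5 requires return to within baseline, a term it does not define. Appendix 9 requires a fixed level for 48 hours and adds an infection condition that 8.1.5 lacks. Exclusion criterion 5 bars entry with a count below 1.5 x 10^9/L. If within baseline means at least the participant's own baseline value, the fixed Appendix 9 level adds little under a cumulative reading, apart from the 48-hour requirement. Result: unclear rather than contradictory.

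6. **Approver.** Section 8.1.5 and the Appendix 9 restart box agree on the Medical Monitor; the Appendix 9 actions list names Medical Governance and points to that restart box. Result: duplicated or unclear naming. It does not by itself change the action on a laboratory result.

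**The case against.** The strongest reply is that the passages refer to one another and should be read together. Section 8.1.1 sends the reader to Appendix 7, Sections 8.1.3 and 3.3.1 send the reader to Appendix 9, and the algorithm that 8.1.1 relies on is a figure that could not be inspected.

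For neutrophil restart this reply largely stands. Appendix 9 introduces its criteria as the only circumstances in which restart may be tried, which makes them necessary, not sufficient. It also defers to what the protocol allows, and Section 8.1.5 points back to it. A reader might infer that the two passages give opposite answers: for instance, that a participant with a baseline of 4.0 x 10^9/L who recovers to 1.6 for 48 hours by day 8, without infection, is cleared by Appendix 9 and refused by 8.1.5. The documents do not support that as a firm contradiction. On the cumulative reading the participant is simply not yet eligible, and the example also assumes a meaning of within baseline that the protocol does not supply. What remains is that the cumulative reading has to be inferred.

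For the two stopping rules the reply does not succeed. Considering a stop and being required to stop immediately cannot be added together, and the discretionary sentence in 8.1.1 is in force whatever the figure shows. Appendix 9 can be read as the actions that follow once 8.1.3 is satisfied, but its own criterion carries no confirmation step, and its repeat count sits alongside the stop rather than before it.

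Two other inferences should be resisted. First, these rules are not the stated mitigation for a listed hepatic risk: the risk table in Section 3.3.1 has no hepatic row. Second, a material effect on the efficacy analysis is not shown. The SAP's Appendix 1 removes per-protocol data, in the final analysis, from the time of stopping when treatment is interrupted for more than 14 days. Sections 8.1.4 and 8.1.5 already cap interruption and restart at 14 days, so that route is remote.

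**Conclusion.** The point holds for two conflicts, liver stopping and neutrophil stopping, and for a lesser defect of clarity in the neutrophil restart conditions and approver. It does not hold for liver restart.

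Its size in participants cannot be calculated, because the documents give no expected frequency for either event. Section 3.3.1 reports no neutrophil decreases below the lower limit of normal in COPD patients treated with danirixin for one year, so the documents give no reason to expect many neutrophil cases. The neutrophil disagreement is also short-lived, since Appendix 9 asks for the repeat within 24 hours. The case for acting is that each result should have one prescribed action at every site.

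The liver conclusion rests on the sentence in Section 8.1.1, assuming the unseen figure does not override it. The neutrophil conclusion rests on Appendix 9's criterion meaning what it states, with no confirmation step implied.

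**What to change.** The sponsor should:

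- reconcile Section 8.1.1 with Appendix 7, and Sections 8.1.3 and 3.3.1 with Appendix 9, so that each pair states the same trigger and action, including whether dosing continues while a repeat neutrophil count is awaited;
- put the neutrophil restart conditions into one list, say explicitly whether all apply, define within baseline, and name one approver;
- alternatively, make Section 8.1 a pure pointer to the appendices with no rule of its own;
- notify sites.

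Which trigger, action or restart condition is right is the sponsor's clinical decision, and none is proposed here. The cost is wording in the next protocol amendment and a clarification letter to sites. SAP Section 3.1.3 shows that the strategic interim has already been run; if dosing has ended, the clinical study report should instead state which rule was applied to each participant who met a liver or neutrophil criterion.
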